## **8.2 Medically-Attended Events and Significant New Medical Conditions**

These classes of events will be collected at all study visits, and if offered spontaneously by the subject at any time.

Medically-attended events (MAEs) are adverse events which result in an unscheduled visit to a healthcare provider due to symptomatic illness or injury. These may include office visits, clinic visits, home consultations, or emergency room evaluations for non-life-threatening events that do not result in hospitalization (life-threatening events or hospitalizations are SAEs, see Section 8.3).

Significant new medical conditions (SNMCs) are adverse events that are new (that is, not present at baseline), clinically significant (meaning that they imply an important change in the subject's long-term health status), and typically chronic (requiring an ongoing change in the subject's medical management). This category is not meant to include minor or transient diagnoses or age-related changes.

The eCRF will provide a field in which the investigator may designate AEs as MAEs, SNMCs, or both. Because of the significance of the designation for the subject's health, long-term medical management, and for evaluation of vaccine safety, SNMCs are expected to be substantiated diagnoses, not isolated symptoms which might or might not be a SNMC, and the investigator should record sufficient data in the eCRF to support the diagnosis.

Full details of MAEs and SNMCs (ie, nature, date of onset, and recovery (if applicable) as well as an assessment of severity, relationship to trial agent, seriousness, treatment, and outcome) will be recorded in the source documentation and captured in the eCRF, and will require the investigator(s) causality assessment.

MAEs and SNMCs will be recorded and summarized from Day 0 to Day 28 for the unblinded data review and from Day 0 to Day 364 following study completion for the final analysis, for all subjects in the Safety Population. Note that MAEs and SNMCs are also included in the overall summary of AEs.

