10.4 Analyses Addressing Protocol Objectives

10.4.1 Analyses of Primary Objectives

10.4.1.1 Safety

Safety analysis will be descriptive and based on the safety population, defined as all subjects who received a dose of trial treatment. Safety will be summarized overall and by individual treatment arms based on solicited short-term reactogenicity post-injection on Day 0, 28-day all AE profile by MedDRA preferred term, and 1-year MAE, SAE, and SNMC profiles

Approved

post-injection on Day 0. All AEs, MAEs, SAEs, and SNMCs will be tabulated by severity, related (possibly, probably, or definitely vs. non-related per investigator assessment), and severe and related. The number and percentage (with 95% CI) of subjects in each treatment group with a given term will be summarized. Clinical laboratory data will be summarized by means and 95% confidence interval (CI), minima and maxima, at Day 0 and Day 28 in each treatment group, as well as means and 95% CI of change from baseline at Day 28. Changes from baseline will also be summarized at Day 28 for each treatment group in terms of the proportion of subjects with no change in toxicity grade versus proportions with 1, 2, or 3 grade changes. A listing and narratives of SAEs will also be produced.

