## 1.1 Study Design

This is a Phase 2, randomized, observer-blinded, active-controlled, dose-finding, formulation-optimizing trial in healthy adults  $\geq 65$  years of age to be conducted in the United States. Up to 1375 eligible subjects will be enrolled and randomized into 1 of 7 treatment groups, as shown in [Table 1](#) below. The base case groups for the demonstration of adjuvant effect, ie, Groups B and E, will each consist of approximately 310 subjects. The remaining groups will consist of approximately 135 (Group D) or 155 (Groups A, C, F, and G) subjects each. Each group will be stratified by site and history of receipt of 2017 - 18 influenza vaccine.

On Day 0, all subjects will receive a study treatment as indicated in [Table 1](#) by intramuscular (IM) injection. Total injection volumes for each treatment group will be 0.5 mL. On Day 28, subjects in Group E will be administered a rescue injection with a 2018 - 19 licensed seasonal influenza vaccine. All other subjects will receive an injection of placebo at Day 28 to maintain trial blind. Trial follow-up for each subject will span approximately 1 year from the Day 0 injection. It is anticipated that a percentage of the randomized trial subjects will not complete the trial. Subjects who withdraw or are discontinued will not be replaced. In addition, all subjects will be offered a 2019 - 20 licensed seasonal influenza vaccine at the last study visit (Day 364).

Enrollment will be divided into 3 stages. Stage 1 will enroll a total of approximately 120 subjects (approximately 20 subjects per treatment group, excluding Group D for which no subjects will be enrolled in Stage 1). Stage 2 will enroll a total of approximately 220 subjects (approximately 20 [Groups A, C, D, F, and G] or 60 subjects [Groups B and E] per treatment group, as per [Table 1](#)). The remainder of the subjects (approximately 1035 subjects total, ie, 115 [Groups A, C, D, F, and G] or 230 [Groups B and E] subjects per treatment group, as per [Table 1](#)) will be enrolled in Stage 3. Progression from Stage 1 to Stage 2 and from Stage 2 to Stage 3 will require favorable review of safety data from the prior stage, against vaccination holding rules.

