### **8.1.2 Unsolicited Adverse Events**

Unsolicited adverse events are defined as any adverse events occurring within the 7-day window following vaccination and not specifically solicited in the diary, or any solicited event that occurs outside the 7-day diary solicitation period. The number (percentage) of subjects with unsolicited AEs will be summarized by MedDRA SOC and PT. All unsolicited AEs will be assessed for severity (Section 8.1.2 in Protocol) and for causality (Section 8.5 in Protocol).

The following summaries of unsolicited AEs will be presented for all subjects in the Safety Population as part of the primary analysis of safety:

- Overall summary of unsolicited AEs by treatment group (Days 0 - 28).
- A summary by severity (normal, mild, moderate, or severe), MedDRA SOC, PT, and treatment group (Days 0 - 28).
- A summary by relationship (causality) to test article of an AE (unlikely/unrelated, possibly, probably, or definitely) to test article, MedDRA SOC, PT, and treatment group (Days 0 - 28).
- A summary of severe and related (unlikely/unrelated, possibly, probably, or definitely) AEs, MedDRA SOC, PT, and treatment group (Days 0 - 28).
- A summary of any AEs including MAEs, SNMCs and SAEs, by MedDRA SOC, PT, and treatment group (Days 0 - 28).

The final analysis will include the following summaries of unsolicited AEs.

- Overall summary of unsolicited AEs by treatment group (Days 0 - 364).
- A summary by severity (normal, mild, moderate, or severe), MedDRA SOC, PT, and treatment group (Days 0 - 364).
- A summary by relationship (causality) to test article of an AE (unlikely/unrelated, possibly, probably, or definitely) to test article, MedDRA SOC, PT, and treatment group (Days 0 - 364).
- A summary of severe and related (unlikely/unrelated, possibly, probably, or definitely) AEs, MedDRA SOC, PT, and treatment group (Days 0 - 364).
- A summary of any AEs including MAEs, SNMCs and SAEs, by MedDRA SOC, PT, and treatment group (Days 0 - 364).

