## **8.3 Serious Adverse Events**

A SAE is defined as an AE that results in any of the following outcomes:

- Death,
- An immediate threat to life,
- In-patient hospitalization or prolongation of an existing hospitalization (Hospitalization is defined as an actual admission, not a 24-hour stay or emergency room visit; note that elective surgeries, undertaken for conditions present prior to receipt of study drug and without complication, should not be considered SAEs),
- A persistent or significant disability/incapacity (substantial disruption of an ability to conduct normal life functions), or

- A congenital anomaly or birth defect (not relevant to this protocol).

The eCRF will provide a field for designating an AE as SAE. SAEs are associated with enhanced reporting requirements (see protocol, Section 8.3).

A listing of subjects with SAEs will be summarized from Day 0 to Day 28 for the unblinded analysis, and from Day 0 to Day 364 following study completion for the final analysis, for all subjects in the Safety Population.

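### The one-year safety tables pool Group E's follow-up before and after its Day 28 licensed vaccine, so the descriptive one-year comparison of Groups B and E is hard to interpret

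*SAP*

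**What the plan says.** SAP 1.1 states that on Day 28 "subjects in Group E will be administered a rescue injection with a 2018 - 19 licensed seasonal influenza vaccine", and that "All other subjects will receive an injection of placebo at Day 28 to maintain trial blind". SAP Table 1 shows Group E as the only Quad-NIV arm without Matrix-M1.

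The final safety summaries run over the whole year by arm. SAP 8.1.2 includes "A summary of any AEs including MAEs, SNMCs and SAEs, by MedDRA SOC, PT, and treatment group (Days 0 - 364", and has companion Days 0-364 tables by severity and by relationship to test article. SAP 8.2 puts MAEs and SNMCs on the same window ("from Day 0 to Day 364 following study completion for the final analysis, for all subjects in the Safety Population"), and SAP 8.3 does so for SAEs. Protocol 10.4.1.1 anchors the "1-year MAE, SAE, and SNMC profiles" to the Day 0 injection.

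The SAP also has an earlier window. Section 8.1.2 specifies five Days 0-28 summaries, beginning with "Overall summary of unsolicited AEs by treatment group (Days 0 - 28". The sentence in 8.2 that sets Day 364 also sets Day 28 for the unblinded review. Section 8.3 says "A listing of subjects with SAEs will be summarized from Day 0 to Day 28 for the unblinded analysis".

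The SAP has no summary that starts at the second injection and no rule for attributing events after it. Section 6.1 summarises exposure to the Day 0 test article only. Section 13 records no change from the protocol's analyses.

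**The concern.** Groups B and E carry the same HA dose and differ by Matrix-M1, so readers will look to them for the adjuvant's safety. The introductions to both documents say that licensure will need a favourable risk-benefit profile for formulations containing Matrix-M1. One-year MAEs, SAEs and SNMCs, with immune-mediated AESIs among them, are primary safety endpoints (SAP 2.2.1).

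From Day 28 the two arms differ in a second respect: Group E has had another active vaccine and Group B has had saline. A single Days 0-364 figure for Group E cannot be read as the experience of unadjuvanted Quad-NIV alone. The relationship table is the least clear, because the SAP does not say which injection a relationship recorded after Day 28 refers to. If the licensed vaccine added events, an adjuvant excess would look smaller. If it prevented illness that would have counted as an MAE, the excess would look larger.

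**Working it through.** **The plan's own safety figures.** SAP 9 gives a probability above 90% of seeing at least one event at true rates of 1.7%, 1.5% and 0.8% with n = 135, 155 and 310. It also gives zero-event one-sided 95% upper bounds of 2.2%, 1.9% and 1.0%.
- 1 - (1 - p)^n gives 90.1%, 90.4% and 91.7%.
- 1 - 0.05^(1/n) gives 2.19%, 1.91% and 0.96%.

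All reproduce. The point concerns table windows and labels, not these figures.

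**Share of Group E follow-up after the second product.** Inputs are 310 subjects, a 364-day window, a nominal second injection at Day 28 and no dropout (assumption).
- Before: 28/364 = 7.7%, or 310 x 28/365.25 = 23.8 person-years.
- After: 336/364 = 92.3%, or 310 x 336/365.25 = 285.2 person-years.
- If the event hazard in the first 28 days is k times the later hazard, the share of events after Day 28 is 336/(336 + 28k). This is 92.3%, 85.7% and 80.0% for k = 1, 2 and 3.

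**The Day 28 boundary.** Protocol 6.1.5 sets the visit at Day 28 ± 2 and allows the injection to be delayed by up to 7 days.
- Injection on Day 26: the rest of Day 26 and all of Days 27 and 28 follow the second product but count in the Days 0-28 tables.
- Injection on Day 28: the rest of that day does the same.
- Injection on Day 35 (28 + 7): Days 29 to 34 still precede the second product but fall outside the Days 0-28 tables. Counted from the latest in-window visit, the delay could reach Day 37 (30 + 7).

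The safety endpoint in SAP 2.2.1 ends at Day 27, while the tables in 8.1.2 include Day 28.

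**Illustration of effect.** The documents give no rate of events caused by the Day 28 vaccine, so the following rests on assumptions. Take a base incidence of 5.5%, within the 5.4% to 6.4% of subjects per group with SAEs in the earlier trial (Protocol 1.8.1, follow-up then ongoing). Take a hypothetical adjuvant excess of 3 points, so B = 8.5% and the true risk ratio is 8.5/5.5 = 1.55. Let r be the net change in Group E from the Day 28 vaccine, so E = 5.5% + r and the pooled difference is 3 - r.

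| r (points) | E | B - E (points) | Risk ratio |
|---|---|---|---|
| -1 | 4.5% | 4 | 1.89 |
| 0 | 5.5% | 3 | 1.55 |
| 1 | 6.5% | 2 | 1.31 |
| 2 | 7.5% | 1 | 1.13 |
| 3 | 8.5% | 0 | 1.00 |

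At r = 0 the 95% half-width of the difference is 1.96 x sqrt(0.085 x 0.915/310 + 0.055 x 0.945/310) = 4.0 points. Shifts of 1 to 3 points therefore lie within the sampling error of this comparison, and nothing in the documents selects a row.

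**The case against.** The strongest reply is that the plan already provides the comparison that matters. The Days 0-28 summaries are by treatment group, cover MAEs, SNMCs and SAEs, and are described as part of the primary safety analysis. Safety is descriptive (SAP 8.1). The B versus E comparison is specified for immunogenicity (SAP 9), and no safety test depends on it. Table 1 defines Group E with its Day 28 injection, so the arm label is not strictly wrong. SAEs are listed and narrated individually, and all eCRF data go into listings.

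Most of this stands. A reader might infer that the early comparison is missing from the SAP; it is not. What remains is the absent later-period summary, the nominal-day cut, the Day 0-only exposure table, and one-year tables that carry no warning about Group E.

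A reader might also infer that pooling biases the B-E difference by a known amount and hides an adjuvant excess. The documents do not support that. No diary follows the Day 28 injection, and only MAEs, SAEs and SNMCs are collected afterwards, so ordinary reactogenicity is largely not added. In the earlier trial about 2% of Fluzone HD recipients sought medical attention for an AE of any cause, and none of 22 SAEs was assessed as related (Protocol 1.8.1). The Day 28 product is not named, so this is only indicative, but it makes an excess of several points hard to assume.

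Nor is the narrower AE collection after Day 28 a bias between arms. It is documented and applies equally to all of them.

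**Conclusion.** The point holds as a matter of reporting and interpretation. Group E's one-year figures combine two active products over a window of which about 92% follows the second, and the SAP neither separates nor labels this. The size and direction of any distortion are unknown, and if the Day 28 vaccine causes no net change in events there is none. Comparisons of Groups A to D with F or G are unaffected, because all six arms receive placebo at Day 28. No test, estimate or decision rule changes.

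Two further inferences should be resisted. One is that the adjuvant-safety statement must rest on 28 days only. One-year follow-up is part of the primary safety objective, and the randomised one-year B versus E data remain informative if reported with the caveat. The other is that Groups F and G can replace E as the later reference for Matrix-M1. They differ from B in antigen as well as adjuvant, and they received licensed vaccine at Day 0. Splitting by onset does not settle causality either, since a late event may still stem from the Day 0 injection.

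**What to change.** Make the following changes to the SAP. The Day 28 injection itself does not change.
- **8.1.2, 8.2 and 8.3:** keep the Days 0-364 summaries. End the early tables at the actual date and time of the Day 28 injection, and add matching tables from that injection to Day 364, with events assigned by onset.
- **Labels:** title Group E's later period 'Quad-NIV then licensed vaccine', and footnote every one-year table, including the relationship table, to the same effect.
- **6.1:** add exposure to the Day 28 injection, by product.
- **Conventions:** state how to assign same-day events without a recorded onset time, partial onset dates (SAP 12.5 imputes several towards Day 0, hence into the first period), and subjects who receive no second injection.
- **Interpretation:** treat the first period as the unconfounded adjuvant-safety comparison, and report the one-year B versus E data alongside it with the caveat.

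The cost is SAP wording and one further set of descriptive tables. Onset dates are already collected, and SAP 3.4.1 already tracks whether the Day 28 rescue injection was given. The clean period remains short, about 24 person-years in Group E, and will say little about late-onset events.

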## **8.3 Serious Adverse Events**

A SAE is defined as an AE that results in any of the following outcomes:

- Death,
- An immediate threat to life,
- In-patient hospitalization or prolongation of an existing hospitalization (Hospitalization is defined as an actual admission, not a 24-hour stay or emergency room visit; note that elective surgeries, undertaken for conditions present prior to receipt of study drug and without complication, should not be considered SAEs),
- A persistent or significant disability/incapacity (substantial disruption of an ability to conduct normal life functions), or

- A congenital anomaly or birth defect (not relevant to this protocol).

The eCRF will provide a field for designating an AE as SAE. SAEs are associated with enhanced reporting requirements (see protocol, Section 8.3).

A listing of subjects with SAEs will be summarized from Day 0 to Day 28 for the unblinded analysis, and from Day 0 to Day 364 following study completion for the final analysis, for all subjects in the Safety Population.

## 8.4 Vital Signs

Descriptive statistics for vital signs (blood pressure, heart rate, oral temperature, respiratory rate) at Days 0, 7, 28, 56, 182 and 364 will be presented by treatment group for all subjects in the Safety Population.

## 9 SAMPLE SIZE CONSIDERATIONS

For safety endpoints, the probability of observing at least 1 adverse event among 135, 155, or 310 subjects for each Quad-NIV formulation is > 90% if the true rate of such events is 1.7%, 1.5%, or 0.8%, respectively. With 135, 155, or 310 subjects for each treatment group, observing no adverse events of interest (eg, vaccine-related SAE) would represent an upper bound of the 1-sided 95% CI on the percentage of such event is 2.2%, 1.9%, or 1.0%, respectively.

This study has a single comparison of 2 treatment groups (Group B vs E) for the primary immunogenicity objective. No formal adjustment for multiple comparisons is planned for the 6 comparisons associated with the 6 strain-specific GMTs. The demonstration of the superiority of Quad-NIV (60 µg HA per A and B strain) co-formulated with 50 µg Matrix-M1 (Group B) as compared to Quad-NIV (60 µg HA per A and B strain) without adjuvant (Group E) requires simultaneous successes of all 6 tests (at least 2 strains meeting the strain-specific superiority criterion and the non-inferiority criterion for the remaining 4 strains). The non-inferiority for this trial will be carried out without a pre-specified margin. Non-inferiority is defined as the 2-sided 95% CI for the ratio of GMTs (Group B / Group E) containing 1.0 (ie, unadjusted 1-sided p-value  $\geq 0.025$  against the null hypothesis of H0: Ratio of GMT  $\leq 1.0$ ). The superiority is defined as the lower limit of the 2-sided 95% CI for the ratio of GMTs (Group B / Group E)  $> 1.0$  (ie, unadjusted 1-sided p-value  $< 0.025$  against the null hypothesis of H0: Ratio of GMT  $\leq 1.0$ ). For other immunogenicity analyses, the purpose is to determine a dose and formulation for the next study based on all available safety and immunogenicity results, including the primary objective analysis. Hence, any statistical analyses (ie, calculations of CIs and p-values) will also be performed without a multiplicity adjustment.

In a previous study using the Tri-NIV formulation (tNIV-E-101), the observed strain-specific standard deviations of log10 HAI titers ranged from approximately 0.4 (B/Brisbane and A/Texas) to approximately 0.6 (A/Switzerland and A/Singapore). Table 6 summarizes power, unadjusted for multiple comparisons, for the primary objective to demonstrate superiority for pair-wise comparisons of the 2 treatment groups. Power calculations also accounted for a 5% attrition rate for the per-protocol population (295 evaluable subjects per treatment group) which is the primary analysis population for all immunogenicity endpoints. For each strain, this study

is designed to detect a 1.4-fold increase (40% increase) in GMTs with  $\geq 84\%$  power. For 2 strains, this study is designed to detect a 1.5-fold increase (50% increase) in GMTs with  $\geq 88\%$  power. For each strain, there will be 97.5% probability of demonstrating a non-inferior GMT for each comparison if 2 treatment groups have an equal GMT. Therefore, demonstrating a superiority against 2 strains with the true difference of 1.5-fold and a non-inferiority against 4 strains with the true difference of 1.0-fold, this study is designed to provide  $\geq 80\%$  power.

**Table 6: Power to Detect Percentage Increase in Ratio of GMTs Between 2 Treatment Groups**

Per-Protocol N Group	Log 10 SD	Fold Increase	Power
295	0.4	1.2	67%
		1.3	93%
		1.4	99%
		1.5	> 99%
		1.6	> 99%
		1.7	> 99%
	0.5	1.2	48%
		1.3	79%
		1.4	94%
		1.5	99%
		1.6	> 99%
		1.7	> 99%
	0.6	1.2	36%
		1.3	63%
		1.4	84%
		1.5	94%
		1.6	98%
		1.7	> 99%

## 10 PRELIMINARY UNBLINDED AND FINAL ANALYSES

An unblinded analysis will be conducted upon completion of all Day 28 visits, which will include all available immunogenicity data through Day 28 at the time of the analysis and safety data (inclusive of clinical laboratory safety assessments) through Day 28. For the review, treatment codes will only be unblinded after all subjects have completed the Day 28 visit, the data are monitored, all applicable queries are resolved, and the database locked.

In order to execute this review, a select group of study staff will be unblinded at the CRO and at Novavax. No individual unblinded at a subject treatment level will be involved in follow-up safety monitoring or immunogenicity determination. Specifically, personnel at the clinical study site including, investigators and study staff, research site, immunology laboratory, and study subjects will remain blinded to treatment assignments until the end of study (ie, Day 384).

Immunogenicity and safety analyses from the Day 28 unblinded analysis may be presented in an abbreviated Unblinded CSR drafted by the Sponsor that will be submitted to regulatory

authorities as needed. The final CSR will present the balance of all disposition, immunogenicity and safety data (inclusive of concomitant medications) through Day 364 (the scheduled end of study).

Any decisions to deviate from the planned analyses stated in SAP will be described in detail in the final study report.

## **11 COMPUTER METHODS**

Statistical analyses will be performed using SAS® version 9.4 or higher in a Windows environment.

Sample size calculations based on two-sample t-test were performed using PASS 12, version 12.0.3 released on August 6, 2013.

